2.3.1 Risk assessment

Table 5 - Risk assessment

Potential risk of clinical significance	Summary of data/rationale for risk	Mitigation strategy
Study intervention(s)		
Infusion reactions including anaphylactic reactions (identified risk) and cytokine release syndrome	
Infusion reactions have been reported as the most common adverse reactions consequent to the IV administration of isatuximab (either as a single agent or in combination with other anticancer agents); this is consistent with the results from clinical studies and from extensive postmarketing experience acquired with other therapeutic mAb proteins. Extensive clinical experience with approved mAbs, in fact, indicates that mild to moderate IR (either allergic, or consisting of cytokine release, which mimics hypersensitivity reactions) are very common, particularly during the first infusion; the cytokine release syndrome associated with mAbs consists of a pseudo allergic Type B (nonimmunoglobulin E mediated) reaction.
 
The infusion reactions with IV isatuximab are most commonly at the first administration, are not dose dependent, and the participants do not appear to sustain sequelae.
 
Infusion reactions generally do not cause therapy discontinuation and tend not to recur at subsequent administrations of isatuximab. Occasionally, these adverse reactions may be serious and systemic (as with anaphylactic reactions, which have been reported throughout the isatuximab IV program). Infusion reactions, however, are most frequently of Grade 1/2 severity and are manageable (for more details on infusion reactions refer to the most recent IB).
 
Similar reactions are expected after SC administration of isatuximab. To allow assessment of these reactions after isatuximab SC versus IV the common term of IRs will be used for this type of reactions after administration of either isatuximab SC or IV.
	
To minimize the incidence and severity of IRs, and as it is done in the isatuximab IV program, all the participants treated with isatuximab SC should routinely receive primary prophylactic treatment. See Section 6.1.2.
 
Participants who do not experience an IR during the first 4 isatuximab administration may have their need for subsequent premedication reconsidered at the Investigator's discretion, except for montelukast which should be administered only on Cycle 1.
 
Details for management of IRs and ISRs after isatuximab SC administration are provided in the Section 6.5.5.

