- b For participants with plasma cells $> 50\%$ of bone marrow nucleated cells at baseline, to initiate Cycle 2, platelet counts should be $\geq 30\,000/mm^3$ regardless response status at end of Cycle 1. During Cycles 2-4, platelet counts should be $\geq 30\,000/mm^3$, if last response is not better than SD, but if last response is PR or better during Cycles 2-4, D1 next cycle can be administered only if platelet counts $\geq 50\,000/mm^3$. For D1 administration beyond Cycle 4, platelet counts should be $\geq 50\,000/mm^3$.
- c A dose delay of up to 14 days between cycles is permitted in order to recover to the participant's baseline status. Beyond 14 days, the participant should be discontinued from study treatment, unless there is strong evidence of clinical benefit to justify continuation of dosing with study treatment (see [Section 6.5.7](#)).
- d If G4 neutropenia, assess ANC every 2-3 days until ANC $\geq 0.5 \times 10^9/L$ and at least weekly thereafter until ANC $\geq 1.0 \times 10^9/L$.

IV: intravenous.
SC: subcutaneous.
PO: per os.

Dose adjustments for participants treated with isatuximab, pomalidomide and dexamethasone combination in the case of non-hematological adverse reaction are shown in [Table 14](#).

Table 14 - Guidelines for dose adjustments for non-hematologic toxicities - isatuximab/pomalidomide/dexamethasone combination

Adverse event	Recommended action		
	Isatuximab^c	Dexamethasone^c	Pomalidomide
DVT/PE			
Grade 3	
Day 1 of cycle: initiate appropriate anticoagulation therapy and when efficient anticoagulation administer cycle at full dose isatuximab and the same dose level of dexamethasone and pomalidomide^a.
 
Within cycle: maintain full dose isatuximab and the same dose level of dexamethasone as planned. For pomalidomide:
 
 First episode: hold pomalidomide, initiate appropriate anticoagulation therapy and restart same dose pomalidomide when efficient anticoagulation. Second episode: despite appropriate anticoagulation pomalidomide permanently discontinued. 		

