Grade 4	
Day 1 of cycle: delay Day 1 administration until controlled and administer the full dose of isatuximab and the same dose level of dexamethasone^a.
 
Within cycle: delay isatuximab and dexamethasone until stabilization and resume without dose reduction at the next planned dates. If delay is >3 days omit isatuximab and dexamethasone until next planned administration.
		Pomalidomide permanently discontinued.
Peripheral Edema			
Grade ≥ 3 (limiting function and unresponsive to therapy or anasarca), excluding infusion associated reaction	
Day 1 of cycle or within cycle: maintain full dose isatuximab as planned.
	
Diuretics as needed, and decrease dexamethasone dose by 1 dose level.
 
if edema persists despite above measures, decrease dose another dose level.
 
If symptoms persist despite second reduction, dexamethasone permanently discontinued.
	
Day 1 of cycle or within cycle: maintain full dose pomalidomide as planned.

Allergic reaction/hypersensitivity			
Grade 2	
Hold study treatment until <Grade 2, and participant clinically stable; then, resume study treatment at the same dose level for infusion reaction related to isatuximab^a.
 
For allergic reaction related to pomalidomide, refer to site local protocol.
 
In case of D-15 at-home administration: transfer participant to investigator site.
		
Grade ≥ 3	Permanent discontinuation of the drug responsible of the allergic reaction.		
Grade ≥ 3 Infections without concomitant neutropenia	
Hold study treatment until systemic treatment of infection complete.
 
Resume all at the same dose level.
		
Herpes zoster	Hold study treatment until lesions are dry, then resume all at the same dose level.		

Adverse event	Recommended action		
	Isatuximab^c	Dexamethasone^c	Pomalidomide
Neuropathy			

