- a A dose delay of up to 14 days between cycles is permitted in order to recover to the participant's baseline status. Beyond 14 days, the participant should be discontinued from study treatment, unless there is strong evidence of clinical benefit to justify continuation of dosing with study treatment (see [Section 6.5.7](#)).
- b See [Section 6.1.2](#) for IR management. Participants may have pomalidomide one or several dose omission at any moment during the cycle.
- c Participants may have isatuximab and/or dexamethasone dose omission within a cycle if certain toxicities do not recover within 3 days following the day of planned infusion (see [Section 6.5](#)).
- d See [Section 6.1.1.3](#) for monitoring of PML and dose modification of study IMPs.

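### A first Grade 3 allergic-type isatuximab infusion reaction means permanent discontinuation under Table 14 but optional resumption under Tables 15 and 16, and the Table 14 row does not exclude it

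*Protocol*

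**What the plan says.** Section 6.5.4, Table 14 (titled "Guidelines for dose adjustments for non-hematologic toxicities"), has an entry for allergic reaction/hypersensitivity. At Grade 3 or higher its only instruction is "Permanent discontinuation of the drug responsible of the allergic reaction". There is no event count, no investigator discretion and no exception. The Grade 2 cell of the same entry says to hold treatment until the reaction improves and then to "resume study treatment at the same dose level for infusion reaction related to isatuximab". It adds one sentence on pomalidomide and one on at-home dosing.

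Section 6.5.5 covers infusion reactions (IRs). For a Grade 3 IR, Table 15 (SC) lets isatuximab resume at the next planned dose, and Table 16 (IV) lets the interrupted infusion restart once the event has improved to Grade 1 or resolved. Both leave this to the investigator, and both require a permanent stop only when a Grade 3 event occurs for the third time. At Grade 4 both stop isatuximab for good.

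Section 2.3.1, Table 5, labels the risk "Infusion reactions including anaphylactic reactions (identified risk) and cytokine release syndrome" and states that "the common term of IRs will be used for this type of reactions after administration of either isatuximab SC or IV".

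**The concern.** The protocol's own terms allow one event to be both an isatuximab IR and an allergic or hypersensitivity reaction. If that event is Grade 3, one table says to stop the drug permanently now, and the table for the participant's arm says the drug may be given again. What is at stake is a safety rule: whether a participant may be re-exposed after a first or second severe allergic-type reaction. Two sites could act differently on the same event, each following a protocol table.

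**Working it through.** The plan states no figure to reproduce on this point, so most of the check is a comparison of texts.

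**1. Required action for isatuximab, by event**

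| Event | Table 14, allergic row | Table 15 (SC) | Table 16 (IV) |
|---|---|---|---|
| First Grade 3 | Permanent stop | May resume at next planned dose | May restart infusion |
| Second Grade 3 | Permanent stop already applied | May resume | May restart |
| Third Grade 3 | Permanent stop already applied | Permanent stop | Permanent stop |
| Grade 4 | Permanent stop | Permanent stop | Permanent stop |

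The number of Grade 3 events that forces a stop is 1 under Table 14 and 3 under Tables 15 and 16. The tables disagree only at the first and second Grade 3 events.

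**2. Does one event fall under both rules?** Yes, on three grounds.
- Section 6.5.5 gives anaphylactic reaction as an example IR term, and Section 8.6.6 gives allergic reaction.
- Table 5 says that IRs can occasionally be serious and systemic, with anaphylactic reactions as its example. The overlap therefore reaches severe events.
- The Grade 2 cell of the Table 14 entry expressly manages isatuximab infusion reactions ("resume study treatment at the same dose level for infusion reaction related to isatuximab"). The entry cannot be read as covering only allergy unrelated to the infusion.

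**3. Does anything in the protocol settle which rule applies?**
- *Exclusion in the row.* There is none. The peripheral edema row directly above carries one, "excluding infusion associated reaction"; the allergic entry does not.
- *Footnote b to Table 14.* It sends the reader to Section 6.1.2 "for IR management. Participants may have pomalidomide one or several dose omission at any moment during the cycle". Section 6.1.2 is the premedication section and has no rule on stopping or restarting after a reaction. The reference should be to Section 6.5.5.
- *Section 6.5, list of tables.* Tables 13 to 16 are named together as recommendations, without an order of precedence.
- *Section 6.5, tie-break.* The instruction to take the most conservative adjustment is written for a participant with several toxicities, and it names reduction, omission and delay. Applied by analogy to one event, it would favour Table 14 and cancel the resumption text of Tables 15 and 16 for allergic-type reactions.
- *Section 7.1.3, rechallenge.* Re-initiation is tied to the investigator judging the product unlikely to be responsible. An isatuximab IR is by definition related to its administration, so this section does not settle the matter.

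**4. How many participants?**
- Input: 2.6% Grade 3 to 4 IRs with IV isatuximab plus pomalidomide and dexamethasone in ICARIA-MM (Section 2.2.3.1).
- Projection to the IV arm: 0.026 × 267 = 6.9, or about 7.
- The denominator of the 2.6% is not stated. The accompanying 38.2% for all IRs does not fit the 154 enrolled (58/154 = 37.7%, 59/154 = 38.3%) but does fit 152 (58/152 = 38.2%). On 152, the 2.6% is about 4 people (0.026 × 152 = 4.0), so the projection is imprecise and is not a ceiling.
- It counts Grade 4 events and non-allergic IRs, which are not in conflict. The Grade 3 allergic share is not given.
- In the Phase 1b study (Section 2.2.3.2) there were 3 IR episodes among 12 + 12 + 10 + 22 = 56 participants, all Grade 2.

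**The case against.** The best case for the plan is that the protocol does say where IRs are managed. Section 6.5.5 states that Tables 15 and 16 describe it, and the mitigation column of Table 5 sends the reader to Section 6.5.5 for SC reactions. Footnote b also sends IR management out of Table 14, although to the wrong section. The Table 14 row keeps a purpose without isatuximab IRs, since it covers whichever drug is responsible, including pomalidomide. The amendment history (Section 10.19) suggests that the Grade 3 resumption rules were introduced deliberately, for consistency with the Investigator's Brochure.

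Much of this stands. Tables 15 and 16 are probably the intended rule, and it would be wrong to say that the protocol gives no direction on IRs. However, none of these places takes IRs out of the Table 14 row, and the Grade 2 cell of that row puts them in. The footnote marker is not visible in the table text available for this review. Even if it sits on the allergic row, it leads to premedication.

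Three stronger readings are not supported.
- A reader might take the Table 5 phrase "either allergic, or consisting of cytokine release, which mimics hypersensitivity reactions" as proof that Grade 3 IRs are allergic events. That sentence concerns mild to moderate reactions to approved antibodies in general. The Grade 3 overlap rests on the grounds in step 2 of the working.
- A reader might infer that investigators are forced into contradictory actions. They are not. The tables are guidelines, resumption is optional, and Section 6.5 lets the investigator discontinue for any adverse event that warrants it. Stopping satisfies all three tables.
- A reader might infer a threat to the trial's conclusions. The numbers in step 4 are too small for a material effect on either co-primary analysis.

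**Conclusion.** The inconsistency is real on the current text but narrow. For a first or second Grade 3 isatuximab IR of allergic or anaphylactic type, Table 14 stops the drug and Tables 15 and 16 permit it to be given again, and no stated rule chooses between them. Grade 4 and the third Grade 3 event are not in conflict.

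The projection of about 7 of 267 IV participants assumes that the ICARIA-MM rate carries over, and it covers all Grade 3 to 4 IRs. The number actually affected is unknown and may be near zero. The point is worth correcting because it concerns re-exposure after a severe reaction and costs almost nothing to settle.

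**What to change.** In Table 14, Grade 3 or higher row of the allergic entry, add: *excluding isatuximab infusion reactions, which are managed under Section 6.5.5, Tables 15 and 16*. In the Grade 2 cell, replace the isatuximab infusion-reaction wording with the same pointer, and keep the sentences on pomalidomide and on at-home administration. Correct footnote b to cite Section 6.5.5.

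This follows the rule that the current text favours. If the sponsor instead wants a permanent stop after a Grade 3 allergic or anaphylactic reaction to isatuximab, that exception should be written into the Grade 3 rows of Tables 15 and 16, with footnote b still corrected. The choice is clinical.

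The cost is two table cells (or one exception in each of two tables) and one cross-reference, made in the next amendment with a letter to sites. No new data or procedures are needed.

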6.5.5 Management of infusion reactions and injection site reactions

Participants should receive premedications prior to isatuximab infusion as detailed in [Section 6.1.2](#) to reduce the risk and severity of IRs commonly observed with mAbs. Infusion associated reactions (including, for example, NCI-CTCAE V5.0 terms “infusion related reaction” or “anaphylactic reaction”) are defined as AEs related to product administration with onset typically within 24 hours from the start of the infusion.

Please refer to the current edition of the IB for IRs manifestations reported in participants treated with isatuximab.

Management of IR and injection sites reactions ISRs is described in [Table 15](#) for SC injection and in [Table 16](#) for IV injections.

Table 15 - Guidelines for management of injection sites reactions (ISRs) and infusion reactions (IRs) for Isatuximab subcutaneous administration NCI-CTCAE v5.0 criteria

Injection site reaction	Infusion reactions	Recommendation
Grade 1 Tenderness with or without associated symptoms (eg, warmth, erythema, itching).	Grade 1 Mild transient reaction; infusion interruption not indicated; intervention not indicated.	ISRs: Continuation of isatuximab administration. Report AE. If the ISRs occurs during or in the 48 hours after at-home administration, subsequent 2 (D15 of subsequent cycle) administrations should be done at the investigator site. IRs: Continuation of isatuximab administration is per the judgment of the Investigator following close direct monitoring of the participant's clinical status. Report AE. Isatuximab administration may be stopped at any time if deemed necessary. If stopped, IR will be classified as Grade 2 as per NCI-CTCAE v5.0 definition.
Grade 2 Pain; lipodystrophy; oedema; phlebitis.	Grade 2 Therapy or infusion interruption indicated but responds promptly to symptomatic treatment (eg, antihistamines, NSAIDS, narcotics, IV fluids); prophylactic medications indicated for ≤24 hours).	ISRs: If during administration: Interrupt isatuximab administration and resume only with an administration with pauses after recovery to G1 or better. Report AE and AESI. In case the reaction occurs during the D-15 at-home administration, definitely stop the at-home injection and contact investigator site. If post-administration: Continue isatuximab treatment after recovery to G1 or better. Report AE and AESI. IRs: If during administration, interrupt isatuximab administration without possibility to restart the current injection. For subsequent cycles, give additional medication with IV diphenhydramine 25 mg IV (or oral equivalent) and/ or IV methylprednisolone 100 mg (or oral equivalent) and/ or other supportive care as needed. Report AE.
Grade 3/4	Grade 3/4	ISRs: Definitive discontinuation of isatuximab administration. Report AE and AESI.

Injection site reaction	Infusion reactions	Recommendation
Grade 3: Ulceration or necrosis severe tissue damage operative intervention indicated.	Grade 3: prolonged (eg, not rapidly responsive to symptomatic medication and/or brief interruption of infusion); recurrence of symptoms following initial improvement; hospitalization indicated for clinical sequelae.	IRs: If during administration: Definitive stop of the current isatuximab administration. Give additional medication with diphenhydramine 25 mg IV (or equivalent) and/or IV methylprednisolone 100 mg (or equivalent) and/or epinephrine as needed. Report AE and AESI. In case of Grade 3, isatuximab administration may be resumed at the next planned administration at Investigator's discretion.
Grade 4: Life-threatening consequences; urgent intervention indicated.	Grade 4: life-threatening consequences; urgent intervention indicated.	If a Grade 3 IR occurs for a 3rd time, treatment with isatuximab will be definitively discontinued for that participant. In case of Grade 4, isatuximab will be permanently discontinued.

Table 16 - Guidelines for management of infusion reactions for isatuximab intravenous administration NCI-CTCAE v5.0 criteria

Infusion reaction grading (NCI-CTCAE V5.0 criteria)	Recommendation
Grade 1: mild transient reaction; infusion interruption not indicated; intervention not indicated.	Continuation of isatuximab infusion is per the judgment of the Investigator following close direct monitoring of the participant's clinical status. Isatuximab infusion may be stopped at any time if deemed necessary. If stopped, IR will be classified as Grade 2 as per NCI-CTCAE definition.
Grade 2: moderate reaction; therapy or infusion interruption indicated but responds promptly to symptomatic treatment (eg, antihistamines, NSAIDS, narcotics, IV fluids); prophylactic medications indicated for ≤24 hours.	Stop isatuximab infusion. Give additional medication with IV diphenhydramine 25 mg IV (or equivalent) and/or IV methylprednisolone 100 mg (or equivalent) as needed. Isatuximab may be resumed only after participant recovery, at half the infusion rate before the interruption, and with close monitoring, and may be increased subsequently, at the Investigator's discretion.
Grade 3 / 4: severe or life-threatening reaction; Grade 3: Prolonged (eg, not rapidly responsive to symptomatic medication and/or brief interruption of infusion); recurrence of symptoms following initial improvement; hospitalization indicated for clinical sequelae. Grade 4: Life-threatening consequences; urgent intervention indicated.	Stop isatuximab infusion. Give additional medication with diphenhydramine 25 mg IV (or equivalent) and/or IV methylprednisolone 100 mg (or equivalent) and/or epinephrine as needed until the resolution of the AE or until the AE improves to Grade 1. Only then, if previous Grade 3, the infusion may be restarted at the Investigator's discretion; if so, the infusion rate should be half of the initial infusion rate and it may be increased subsequently, at the Investigator's discretion. If the severity of an infusion-related AE returns to Grade 3 after the restart of the infusion, the same procedure described above may be repeated at the Investigator's discretion. If a Grade 3 infusion-related AE occurs for a 3rd time, treatment with isatuximab will be definitely discontinued for that patient. In case of Grade 4, isatuximab will be permanently discontinued.

6.5.6 Tumor lysis syndrome

Tumor lysis syndrome may occur and is a life-threatening event. The participants at greatest risk of TLS are those with high tumor burden prior to treatment. These participants should be monitored closely, and appropriate precautions should be taken (such as use of prophylactic uric acid lowering agents [eg, allopurinol or rasburicase], regular measurement of electrolytes).

Tumor lysis syndrome has to be managed according to site usual practice. [Table 17](#) provides some parameters to be checked in case of TLS suspicion and high-level recommendations for TLS management. Abnormalities listed in [Table 17](#) do not support TLS diagnosis exclusively and any differential diagnosis also needs to be assessed if appropriate.

After recovery, study treatment can be re-administered as planned at the same dose.

Table 17 - Management of tumor lysis syndrome

TLS main possible diagnosis criteria	Recommended action
Laboratory TLS: ≥2 simultaneous abnormalities within 3 days prior to and up to 7 days after treatment start: 
• Uric acid >8 mg/dL (>475.8 µmol/L).• Potassium >6.0 mmol/L.• Phosphate >4.5 mg/dL (>1.5 mmol/L).• Corrected calcium <7.0 mg/dL (<1.75 mmol/L), ionized calcium <1.12 mg/dL (0.3 mmol/L)^a.	Omit study treatment until all serum chemistries have resolved. Ensure adequate hydration, correct laboratory abnormalities, fluid overload, uric acid lowering agents (such as rasburicase), electrolyte, or acid-base deviation.
Clinical TLS: Laboratory TLS in addition to 1 of the following complications: 
• Acute kidney injury: Increase in the serum creatinine level of 0.3 mg/dL (26.5 µmol/L) or the presence of oliguria, defined as an average urine output of <0.5 mL/kg/hour for 6 hours.• Seizures, sudden death, cardiac dysrhythmia, neuromuscular irritability (tetany, paresthesias, muscle twitching, carpopedal spasm, Trouseau's sign, Chvostek's sign, laryngospasm, bronchospasm), hypotension, or heart failure probably or definitely caused by hypocalcemia.• Dysrhythmias probably or definitely caused by hyperkalemia.	Monitor TLS complications including renal functions. Reinstitute study treatment at full dose after resolution.

^a The corrected calcium level in milligrams per deciliter = measured calcium level in milligrams per deciliter + 0.8 × (4-albumin in grams per deciliter). Adapted from Howard et al.

